7.2.3 Other baseline characteristics

Baseline patient data relating to disease factors include:

- Date of diagnosis and stage of CRC
- ECOG performance status
- Prior antineoplastic therapies
- Laboratory results
- ECG findings
- Incidence of previous HFSR will be recorded as “yes/no”; no chart review is required.

All medications and significant non-drug therapies taken within 14 days before study entry must be recorded in the CRF, including:

- Medication trade name and dose
- Reason for medication
- Start Date and End date or if continuing at time of study entry.

7.3 Efficacy

Phase II Study of Perindopril and Regorafenib in mCRC (PARICCA)

The primary endpoint of this trial is a safety endpoint. Efficacy measurement in this study will be assessed as a secondary endpoint, and will be measured by assessing progression-free survival (PFS). PFS will be evaluated based on RECIST v1.1 criteria, 20% progression or any new lesion.

Measurements will be made at baseline and then every 8 weeks during the treatment period until progressive disease is documented, and also at the end of treatment visit if applicable. At baseline, information on all potential sites of tumor lesions should be obtained, at a minimum patients must have a radiologic examination of chest, abdomen and pelvis. Throughout the study period, the same lesions to those identified and measured at baseline must be evaluated using the same technique, the identical contrast agent and the same slice thickness. If additional lesions are suspected, the relevant anatomical regions should be evaluated by appropriate radiologic examinations.

If a patient discontinues treatment prematurely before progression (e.g., due to toxicity), the investigator should perform a complete physical, laboratory and radiological assessment as soon as possible after study drug discontinuation. After treatment discontinuation, tumor assessments should be continued until progression, even if the patient receives other treatments.

For the purposes of defining progressive disease, every effort should be made to obtain radiographical imaging at the defined timepoints.

In cases where radiographic imaging is not possible, clinical progression may be used. Clinical progression is based on the judgment of the investigator.

The complete list of variables to be analyzed for this study will be provided in the statistical analysis plan.

7.5 Safety

Although we are assuming that the co-administration of perindopril with regorafenib will mitigate HFSR symptoms, this may not be the case. Grade 3 HFSR rate will be evaluated after the first 10 patients have completed at least one cycle of regorafenib. If a significantly higher rate of grade 3 HFSR is seen in these first 10 patients i.e. Grade 3 is seen in more than 5 out of the 10 patients, the study will be discontinued.

Safety variables for **regorafenib** are as follows: adverse events, laboratory changes (hematology, clinical chemistry and clinical urinalysis), changes in vital signs (blood pressure, heart rate, respiratory rate, temperature) and electrocardiogram (ECG). These will be measured as per standard of care for regorafenib, as per study schedule (Table 7). See more details from product monograph below.

Phase II Study of Perindopril and Regorafenib in mCRC (PARICCA)

Safety variables for **perindopril** can be obtained from the COVERSYL® Product Monograph. The most frequent adverse reactions observed with perindopril are: cough, dizziness, headache, asthenia, gastro-intestinal disorders (abdominal pain, nausea, dyspepsia). The most serious adverse reactions are: hypersensitivity reaction (angioedema), renal dysfunction (in high risk patients), pancreatitis, blood disorders (pancytopenia, agranulocytosis, and thrombocytopenia). During the long-term safety assessment in heart failure patients, the severe adverse events occurring with the highest frequency were angina pectoris and orthostatic hypotension. The most severe drug reactions from post-marketing experience were pancreatitis and blood disorders (pancytopenia, agranulocytosis, and thrombocytopenia).

More detailed safety variables from the regorafenib monograph include:

Regorafenib has been associated with an increased incidence of electrolyte abnormalities (including hypophosphatemia, hypocalcemia, hyponatremia and hypokalemia) and metabolic abnormalities (including increases in thyroid stimulating hormone, lipase and amylase). The abnormalities are generally of mild to moderate severity, not associated with clinical manifestations, and do not usually require dose interruptions or reductions. It is recommended to monitor biochemical and metabolic parameters during regorafenib treatment and to institute appropriate replacement therapy according to standard clinical practice if required. Dose interruption or reduction, or permanent discontinuation of regorafenib should be considered in case of persistent or recurrent significant abnormalities.

Since drugs with anti-angiogenic properties may suppress wound healing, treatment with regorafenib should be stopped at least 2 weeks prior to scheduled surgery. The decision to resume regorafenib after surgery should be based on clinical judgment of adequate wound healing. Regorafenib should be discontinued in patients with wound dehiscence.

Regorafenib may decrease heart rate. Caution should be observed in patients with a low heart rate at baseline (< 60 beats per minute), a history of syncope or arrhythmia, sick sinus syndrome, sinoatrial block, atrioventricular (AV) block, ischemic heart disease, or congestive heart failure.

Patients with a history of ischemic heart disease should be monitored for clinical signs and symptoms of myocardial ischemia. In patients who develop new or acute onset cardiac ischemia and/or infarction regorafenib should be withheld until resolution. The decision to re-initiate regorafenib therapy should be based on careful consideration of the potential benefits and risks of the individual patient. Regorafenib should be permanently discontinued if there is no resolution.

Phase II Study of Perindopril and Regorafenib in mCRC (PARICCA)

Regorafenib should be permanently discontinued in patients who develop gastrointestinal perforation or fistula.

Treatment with regorafenib should be stopped in patients with severe or life threatening hemorrhage. Patients receiving warfarin should be closely monitored.

For patients with observed worsening of liver function tests, dose modification (interruption, reduction) or discontinuation of regorafenib is recommended.

In case of unexplained respiratory symptoms such as non-productive cough, dyspnea, crackles, or radiological pulmonary infiltrates, regorafenib should be discontinued until further pulmonary investigation excludes interstitial lung disease and pneumonitis.

Patients with severe hepatic impairment will be excluded. Closely monitor patients with any hepatic impairment for adverse reactions, discontinuation of regorafenib, along with control of hypertension and supportive medical management of other symptoms is recommended.

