Grade 1: Numbness, dysesthesia, paraesthesia, tingling, painless swelling, erythema or discomfort of the hands or feet which does not disrupt the subjects normal activities	Any	Maintain dose level and institute immediately supportive measures for symptomatic relief
Grade 2: Painful erythema and swelling of the hands or feet and/or discomfort which affects the subject's normal	1st occurrence	Consider decreasing dose by one dose level and institute immediately supportive measures. If no improvement, interrupt therapy for a minimum

Phase II Study of Perindopril and Regorafenib in mCRC (PARICCA)

Table 4 Dose Modifications for Hand-Foot Skin Reaction		
Skin Toxicity Grade (according to CTCAE version 4.03 "Palmar-plantar erythrodysesthesia syndrome")	Occurrence ^c	Suggested Dose Modification ^c
activities		of 7 days, until toxicity resolves to Grade 0-1. ^b
	No improvement within 7 days or 2nd occurrence	Interrupt therapy until toxicity resolves to Grade 0-1. When resuming treatment, treat at reduced dose level. ^b
	3rd occurrence	Interrupt therapy until toxicity resolves to Grade 0-1. When resuming treatment, decrease dose by one additional dose level. ^{a,b}
	4th occurrence	Discontinue therapy
Grade 3: Moist desquamation, ulceration, blistering or severe pain of the hands or feet, or severe discomfort that causes the subject to be unable to work or perform activities of daily living.	1st occurrence	Institute supportive measures immediately. Interrupt therapy for a minimum of 7 days until toxicity resolves to Grade 0-1. When resuming treatment, decrease dose by one dose level. ^b
	2nd occurrence	Institute supportive measures immediately. Interrupt therapy for a minimum of 7 days until toxicity resolves to Grade 0-1. When resuming treatment, decrease dose by one additional dose level. ^{a,b}
	3rd occurrence	Discontinue treatment permanently.
^a Subjects requiring > 2 dose reductions (< 80mg) should go off protocol therapy ^b If toxicity returns to Grade 0-1 after dose reduction, dose re-escalation is permitted at the discretion of the investigator ^c A more conservative dose modification approach, if medically indicated, is acceptable, but please contact the sponsor prior to making any changes.		

If no recovery after a 4-week delay, treatment will be discontinued permanently.

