8.3.2 Statistical hypothesis and method of analysis

The primary analysis will be a comparison of the proportion of patients with any grade HFSR toxicity to 47% using the normal approximation z-test statistic and 2-sided 5% significance level. The statistical hypotheses are

H0: $P = 0.47$ versus H1: $P \neq 0.47$

where P is the proportion of any grade HFSR toxicity.

The study includes a single interim safety analysis after 10 patients have completed the study medication.

The proportion of patients having worst grade 3 HFSR toxicity will be determined along with the 95% confidence interval.

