8.6 Planned interim analyses

A single interim analysis is planned to be performed at the point that 10 patients have completed their first cycle of study treatment. This will be to determine if the study should continue. The study will be discontinued if 5 out of the first 10 patients exhibit a Grade 3 HFSR. The lower bound limit of the 95% confidence interval would be 18.7% which is higher than the 17% of patients who experienced HFSR grade 3 severity in the CORRECT trial.

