9.5 Archiving

Essential documents shall be archived safely and securely in such a way that ensures that they are readily available upon authorities' request.

Patient (hospital) files will be archived according to local regulations and in accordance with the maximum period of time permitted by the hospital, institution or private practice. Where the archiving procedures do not meet the minimum timelines required by the sponsor, alternative arrangements must be made to ensure the availability of the source documents for the required period.

Phase II Study of Perindopril and Regorafenib in mCRC (PARICCA)

The investigator/institution notifies the sponsor if the archival arrangements change (e.g. relocation or transfer of ownership). The investigator site file is not to be destroyed without the sponsor's approval.

The investigator's contract will contain all regulations relevant for the study center.

10. Premature termination of the study

The study will be discontinued if 5 of the first 10 patients exhibit a Grade 3 or higher HFSR. Note that in the CORRECT trial, 47% of patients experienced HFSR of all grades with 17% experiencing HFSR with grade 3 severity.

(Note: Given the small patient numbers (n=10) for the interim analysis and using the expected number from CORRECT, there would be ~2 expected with HFRS at Grade 3. If you have n≥3 to discontinue the study, that may be problematic given a single patient can have a significant impact at such low numbers. Increasing it to 5 would indicate there is a signal suggesting a ≥2 fold increase in grade 3 HFSR events and study should be discontinued.)

The sponsor/Investigator has the right to close this study at any time, which may be due but not limited to the following reasons:

- If risk-benefit ratio becomes unacceptable owing to, for example,
 - Safety findings from this study (e.g. SAEs)
 - Results of any interim analysis
 - Results of parallel clinical studies
 - Results of parallel animal studies (on e.g. toxicity, teratogenicity, carcinogenicity or reproduction toxicity).
- If the study conduct (e.g. recruitment rate; drop-out rate; data quality; protocol compliance) does not suggest a proper completion of the trial within a reasonable time frame.

For any of the above closures, the following applies:

- Closures should occur only after consultation between involved parties.

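### The one prespecified HFSR stopping look is tied to patients who have completed a cycle, so a patient who permanently stops in cycle 1, including for grade 3 HFSR, can be left out of the ten counted

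*Combined protocol and SAP*

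**What the plan says.** There is one planned look at grade 3 HFSR. Three sections time it, each on a form of completion:

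- Section 7.5: "Grade 3 HFSR rate will be evaluated after the first 10 patients have completed at least one cycle of regorafenib". The threshold follows: "If a significantly higher rate of grade 3 HFSR is seen in these first 10 patients", spelled out as "Grade 3 is seen in more than 5 out of the 10 patients, the study will be discontinued".
- Section 8.3.2: "The study includes a single interim safety analysis after 10 patients have completed the study medication".
- Section 8.6: "A single interim analysis is planned to be performed at the point that 10 patients have completed their first cycle of study treatment".

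The stopping sentences elsewhere carry no completion condition. Section 8.6 continues: "The study will be discontinued if 5 out of the first 10 patients exhibit a Grade 3 HFSR". Section 10 states, as does the Synopsis: "The study will be discontinued if 5 of the first 10 patients exhibit a Grade 3 or higher HFSR".

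Section 8.2 defines a safety set of everyone who received at least one dose, but the interim rule does not refer to it. No section defines a completed cycle, or says how a patient who stops or interrupts during cycle 1 enters the count. Section 3.1 records that a data monitoring committee does not apply.

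**The concern.** A stopping rule needs a fixed denominator. Here the ten can be the first ten treated or the first ten to complete a cycle. The two sets differ as soon as one patient leaves during cycle 1.

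The loss can be related to the event being monitored. Section 1.4 notes that first symptoms can appear after 5 to 7 days on therapy. For a first grade 3 HFSR, Table 4 in Section 6.4.2 says "Interrupt therapy for a minimum of 7 days until toxicity resolves to Grade 0-1". Section 5.2.1 lets the investigator withdraw a patient for a sufficiently serious adverse reaction at any time. A patient who stops for good in cycle 1 because of grade 3 HFSR has had the event, yet under the literal text of Section 7.5 is not among the ten.

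Sections 1.5 and 4 commit to discontinuing the study if HFSR is more severe with perindopril than with regorafenib alone. This look is the only place where that commitment is given a number.

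**Working it through.** **The plan's own figure.** Section 8.6 gives 18.7% as the lower 95% limit for 5 of 10. The exact (Clopper-Pearson) interval for 5/10 is 18.7% to 81.3%, so the figure reproduces. The problem is one of definition, not of arithmetic.

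**The texts side by side.**

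| Place | When the look is held | Who is counted | Threshold |
|---|---|---|---|
| Synopsis | not stated | first 10 patients | 5 |
| 7.5 | first 10 have completed at least one cycle of regorafenib | those first 10 | more than 5 |
| 8.3.2 | 10 have completed the study medication | not stated | not stated |
| 8.6 | 10 have completed the first cycle | first 10 patients | 5 |
| 10 | not stated | first 10 patients | 5 |

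**Effect of one substitution.** Suppose five of the first ten treated have grade 3 HFSR, and one of those five stops in cycle 1 and is replaced by a completer without the event. The count becomes 4/10. Its exact lower limit is 12.2%, below the 17% reference in Section 8.6, and neither threshold is met.

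**Effect on the chance of stopping.** Inputs:

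- p, the true grade 3 rate: 17% is the reference in Section 8.6. Section 10 says the rule should signal at least a two-fold increase, and 2 × 17% = 34%. Rates of 40% and 50% are added for illustration.
- s, the share of grade 3 patients not counted, and t, the share of other patients not counted: the documents give neither, so both are assumed over a range.

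The rate among those counted is q = p(1−s) / [p(1−s) + (1−p)(1−t)]. The chance of reaching the threshold is P(X ≥ 5) with X ~ Binomial(10, q).

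Example: p = 0.34, s = 0.25, t = 0 gives q = 0.255 / (0.255 + 0.66) = 0.279 and P(X ≥ 5) = 11.6%.

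| True rate p | All treated counted | s=10%, t=0 | s=25%, t=0 | s=50%, t=0 |
|---|---|---|---|---|
| 34% | 22.7% | 18.1% | 11.6% | 3.6% |
| 40% | 36.7% | 30.6% | 21.3% | 7.8% |
| 50% | 62.3% | 55.7% | 44.0% | 21.3% |

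Under the threshold in Section 7.5 (more than 5), the 34% row is 8.4%, 6.1%, 3.3% and 0.7%.

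**Sensitivity to loss of other patients,** at p = 40% with at least 5 of 10:

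- s = 25%, t = 0: 21.3%
- s = 25%, t = 10%: 26.4%
- s = t: 36.7%, no bias
- s = 5%, t = 10%: 40.0%, bias reversed

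**The case against.** The strongest reply is that completion is only a clock. Section 8.6 separates the timing sentence from the stopping sentence, and the stopping sentences in the Synopsis, 8.6 and 10 name the first 10 patients without qualification. On that reading the ten are the first ten treated and nobody is lost. This is a reasonable reading, but the protocol does not state it, and the back-reference in Section 7.5 points to the completers. Exclusion is therefore permitted by the text, not required by it.

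Several stronger conclusions that a reader might draw are not supported:

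- **That every grade 3 patient drops out of the count.** Table 4 has a first grade 3 event interrupt treatment and then resume it. A cycle is 28 days, and no section requires 21 days of dosing for a cycle to be complete. An interrupted patient may well be counted; permanent stopping in cycle 1 is the clear case.
- **That one early leaver means the look never happens.** Section 8.6 needs 10 patients to complete a cycle, so an early leaver only delays it.
- **That the count no longer matches the CORRECT rate of 17%.** The documents do not say how that trial counted its patients, so a mismatch is not shown.
- **That bias towards continuing is established.** Its direction depends on who is lost, as the sensitivity figures show.

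Other protections also exist. Adverse events are assessed weekly over days 1 to 21 of cycle 1, early leavers remain in the safety set, and Section 10 lets the sponsor close the study at any time. These stand, but none supplies a prespecified count.

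**Conclusion.** The concern holds as a defect of definition. The only prespecified numeric HFSR stopping rule has a counted set that differs between sections. Followed literally, Section 7.5 leaves out a patient who permanently stops in cycle 1, including one who stops for the event being monitored.

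If grade 3 patients are lost more often than others, the look is biased towards continuing. At a doubled rate of 34% and a threshold of at least 5, losing 10% or 25% of grade 3 patients and no others costs 4.6 or 11.1 percentage points of a 22.7% chance of stopping (22.7 − 18.1 and 22.7 − 11.6). These sizes rest wholly on assumed loss shares. The possibility of miscounting rests on the text alone. The primary test and the 18.7% limit for an observed 5 of 10 are unaffected.

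**What to change.** Use one population and one trigger in the Synopsis and Sections 7.5, 8.3.2, 8.6 and 10:

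1. The ten are the first 10 patients who received at least one dose, in line with the safety set in Section 8.2.
2. The look is held when each of them has either reached the end of the 28-day cycle 1 period, whatever dose was taken, or permanently stopped treatment.
3. Every grade 3 or higher HFSR among those ten is counted, including in patients who interrupted or stopped.

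The sponsor must separately reconcile the threshold of 5 (Synopsis, 8.6, 10) with more than 5 (7.5). No threshold is proposed here, and no dosing or treatment rule changes.

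The cost is wording in five places. No extra patients or data are needed, and the look would come no later than one that waits for ten completers.

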Details for the premature termination of the study are provided in Section 10 (Premature termination of the study).

For all subjects who discontinue study treatment, relevant visit data will be entered into the case report form and any unused study drug will be accounted for and returned. Adverse events or clinical laboratory abnormalities that cause a patient to discontinue from study treatment should be followed until they recover or stabilized.

All subjects will enter the follow-up period upon discontinuation of the treatment drugs. Regardless of the reason for discontinuation all subjects will be followed for survival until death is documented, except for those who specifically withdraw consent to follow-up. Subjects who withdraw consent from study drug treatment may enter the Follow-up Period.

Assessment of survival status will be performed approximately every month. In addition, for subjects, who discontinue study treatment and have not experienced PD, available tumor assessments will be recorded in the CRF until PD is documented.

Phase II Study of Perindopril and Regorafenib in mCRC (PARICCA)

Death due to mCRC is not a serious adverse event. If any patient should die during the study treatment or within 30 days of their last dose of study drug, of causes NOT related to the disease itself (mCRC), the Investigator or a designated associate(s) will inform the Bayer HealthCare Medical hotline. If the cause of death is not related to the disease itself (mCRC), the cause of death should be recorded in detail within 24 hours of notification to the investigator on a Serious Adverse Event Form and transmitted to Health Canada.

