11.1 Ethical and legal conduct of the study

The procedures set out in this protocol, pertaining to the conduct, evaluation, and documentation of this study, are designed to ensure that the sponsor and investigator abide by Good Clinical Practice (GCP) guidelines and under the guiding principles detailed in the Declaration of Helsinki. The study will also be carried out in keeping with applicable local law(s) and regulation(s).

Documented approval from appropriate IEC(s)/IRBs will be obtained for the center before start of the study, according to GCP, local laws, regulations and organizations. When necessary, an extension, amendment or renewal of the EC/IRB approval must be obtained. The Sponsor/Investigator will ensure a list of the EC/IRB members involved in the vote, and a statement to confirm that the EC/IRB is organized and operates according to GCP and applicable laws and regulations, is filed with the study documents.

Strict adherence to all specifications laid down in this protocol is required for all aspects of study conduct; the investigator may not modify or alter the procedures described in this protocol. However, the Sponsor/Investigator may implement a deviation from, or a change of, the protocol to eliminate an immediate hazard(s) to the trial subjects without prior IEC/IRB approval/favorable opinion. As soon as possible, the implemented deviation or change, the reasons for it and if appropriate the proposed protocol amendment should be submitted to the IEC/IRB.

Any deviations from the protocol must be explained and documented by the investigator. Details on discontinuation of the study can be found in Section 10.

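### Section 7.5 stops the trial only at six or more grade 3 HFSR cases in ten, where the Synopsis and Sections 8.6 and 10 stop at five; Section 8.3.2 also times the look differently

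*Combined protocol and SAP*

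**What the plan says.** The rule for stopping the trial on grade 3 HFSR appears in four places.

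- Section 7.5 evaluates the grade 3 rate once the first ten patients have had at least one cycle. It describes the trigger as a significantly raised rate and then spells that out: if "Grade 3 is seen in more than 5 out of the 10 patients, the study will be discontinued".
- Section 8.6: "The study will be discontinued if 5 out of the first 10 patients exhibit a Grade 3 HFSR". It gives a reason: "The lower bound limit of the 95% confidence interval would be 18.7% which is higher than the 17% of patients" with grade 3 HFSR in the CORRECT trial.
- Section 10: "The study will be discontinued if 5 of the first 10 patients exhibit a Grade 3 or higher HFSR". A note there explains that about two cases would be expected in ten patients, rejects three as too sensitive to a single patient, and settles on five: "Increasing it to 5 would indicate there is a signal suggesting a ≥2 fold increase in grade 3 HFSR events".
- The Synopsis (Duration of treatment) repeats the Section 10 rule.

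Two cross-references send the reader to Section 10 for termination: "Details for the premature termination of the study are provided in Section 10" (Section 5.2.1) and "Details on discontinuation of the study can be found in Section 10" (Section 11.1).

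On timing, Section 8.6 places the look when ten patients have finished their first cycle, which agrees with Section 7.5. Section 8.3.2 differs: "The study includes a single interim safety analysis after 10 patients have completed the study medication". Under Sections 4 and 6.1, treatment has no set length; it runs to progression, unacceptable toxicity or withdrawal.

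**The concern.** More than five of ten means at least six, so the sections disagree at exactly five. All of this is current text, not the summary of changes.

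The rule is the trial's only numeric stopping criterion. It is applied once, and Section 3.1 says a data monitoring committee does not apply. The other study-level grounds do not settle a 5/10 result. Sections 1.5 and 4 say the study will stop if HFSR proves more severe than with regorafenib alone, but give no number. The remaining grounds in Section 10 are discretionary. An investigator who turns to the Safety section would find that the rule has not been met at the very count that Sections 8.6 and 10 were written to catch.

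The timing conflict matters for the same reason. A look that waits for ten patients to come off treatment will generally fall later than one tied to the first cycle, and more patients could start the combination before it.

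**Working it through.** **Inputs.** n = 10 (Sections 7.5, 8.6 and 10). Reference grade 3 rate 17% (Sections 1.2 and 8.6). Cut-offs: at least 5 (Synopsis, 8.6, 10) and at least 6 (7.5). Reading five of ten as at least five is an interpretation; the Section 10 note supports it by comparing five with a rule of three or more.

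**Step 1: reproduce the 18.7%.** The exact (Clopper-Pearson) two-sided 95% lower limit for x cases in n is the 0.025 quantile of Beta(x, n − x + 1):

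- x = 4: Beta(4, 7) gives 12.2%
- x = 5: Beta(5, 6) gives 18.7%
- x = 6: Beta(6, 5) gives 26.2%

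The figure in Section 8.6 is therefore the exact limit for 5/10. Other intervals for 5/10 do not match it (Wald 19.0%, Wilson 23.7%). Five is also the smallest count whose exact lower limit exceeds 17%, since 4/10 gives 12.2%. So 5/10 already meets the condition of a significantly raised rate in Section 7.5, although the count given there leaves it out.

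**Step 2: probability of stopping.** With X ~ Binomial(10, p), the two rules differ only at X = 5, where P(X = 5) = 252 × p⁵ × (1 − p)⁵:

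- p = 0.17: 252 × (0.17 × 0.83)⁵ = 252 × 0.1411⁵ = 0.0141
- p = 0.34: 252 × (0.34 × 0.66)⁵ = 252 × 0.2244⁵ = 0.1434
- p = 0.50: 252 / 1024 = 0.246

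| True grade 3 rate | P(X ≥ 5) | P(X ≥ 6) | P(X = 5) |
|---|---|---|---|
| 17% (reference) | 1.7% | 0.3% | 1.4% |
| 34% (2 × 17%, illustrative) | 22.7% | 8.4% | 14.3% |
| 50% (illustrative) | 62.3% | 37.7% | 24.6% |

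At 34%, 0.1434 / 0.2270 = 63% of the trials that would stop under the rule of five would not trigger under Section 7.5.

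**Step 3: timing.** Section 8.6 fixes the look at the end of one 28-day cycle. Section 8.3.2 ties it to the end of treatment. Table 7 expects 2 to 4 cycles, so a typical patient's end of treatment falls (2 − 1) = 1 to (4 − 1) = 3 cycles after the first, or 28 to 84 days. Section 1.6 expects about four months on trial. The calendar delay of the look itself also depends on accrual, for which the protocol gives no rate, so it cannot be derived.

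**The case against.** The best counter-argument is that the protocol resolves the threshold itself. Section 7.5 does not order the study to continue at five, so at 5/10 the only express instruction is to stop. Three places agree on five, two cross-references point to Section 10, and both Section 8.6 and Section 10 justify five. On this view Section 7.5 contains a slip of wording. For timing, Section 8.6 is the section devoted to the interim analysis, while Section 8.3.2 mentions it in one line.

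Much of this stands. Section 7.5 under-specifies the trigger and issues no contrary command, and the intent is recoverable. But no clause gives Section 10 precedence, and Section 7.5 is worded as a rule in its own right, so knowing the intent tells us how to edit it without removing the conflict.

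On size, three points are fair. A result of exactly 5/10 is rare (1.4%) at the reference rate, and stops lost there would be false alarms, so the 17% row is no measure of harm. The 34% rate is an assumption: Section 10 speaks of a twofold signal but sets no alternative. And even the intended rule stops only 22.7% of the time at 34%. None of this makes the wording in Section 7.5 right.

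Individual patients also remain protected by the HFSR dose rules in Table 4 and by weekly first-cycle visits. The primary test and the sample size of 34 are unaffected.

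**Conclusion.** The inconsistency is real and Section 7.5 is wrong as written. The arithmetic in Section 8.6 and the argument in Section 10 both belong to a cut-off of five. Read literally, Section 7.5 cuts the chance of stopping from 22.7% to 8.4% if the true grade 3 rate is 34%, and from 62.3% to 37.7% if it is 50%; at 17% the change is from 1.7% to 0.3%. These figures assume independent patients, ten evaluated at the look, and five read as five or more; 34% and 50% are illustrative.

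Section 8.3.2 is a second, separate conflict: it ties the safety look to an event with no fixed date, by expectation one to three cycles later per patient than the time point in Section 8.6. Because this is the only numeric stopping rule and there is no monitoring committee, both should be corrected.

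**What to change.** Make two edits:

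1. In Section 7.5, change the trigger from more than 5 to *5 or more* of the first 10 patients.
2. In Section 8.3.2, time the interim safety analysis at completion of the first cycle by ten patients, matching Section 8.6.

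Keep the 18.7% limit in Section 8.6 and the rationale in Section 10 unchanged. Writing *5 or more* in the Synopsis, Section 8.6 and Section 10 as well would be a useful but optional clarification.

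The cost is a wording amendment in two places, with no extra patients or procedures and no change to the primary analysis or sample size.
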